## REVISION HISTORY

**Title:** Eyefree Clinical Study Protocol

**Device name:** EyeControl

**Version number: 01, dated 16May2016**

**Previous version number: N/A**

## Summary of Changes

Rev.	Page/Section	Description of change	Reason for change
1	---	First issue	---

**Print Name**
**Signature**
**Date**

## PROTOCOL SYNOPSIS

Sponsor:	Eyefree assistive communication Ltd, [name] [contact]
Protocol title:	Safety and Feasibility of the EyeControl device (eye-based communication device) for ALS patients.
Protocol number:	CLN-001
Study Purpose/objective:	To demonstrate the safety and feasibility of the EyeControl device in healthy volunteers, and ALS patients in early stages.
Study phase:	First in Human – Proof of concept
The Device:	
The EyeControl device is an eye movement-based communication device in the form of wearable glasses with connected infrared camera that tracks the pupil and translates blinks and movements into commands.
 
The camera communicates with a small computer called "Odroid" via USB.
 
The "Odroid" translates the user's eyes movements into commands and can transmit the commands to three outputs: an earphone, a speaker and a smartphone via Bluetooth.
 
The smartphone runs an application which enables the patient to communicate.
 
An algorithm is used to allow for a quick auto- calibration of the device, so that the patient does not need assistance in order to do so.
 
The device is currently based on a 3-steps solution:
 
 
1. Alert sound - calling for assistance.
 
2. Predefined sentences - such as "I'm hot", "my hand hurts" etc.
 
3. Composing sentences - (similar to SMS).
 

Study Design:	
The study will be conducted in 2 enrollment stages. Initially, up to 10 healthy volunteers will be recruited and go through a short training for the use of the device followed by actual controlled use of several hours. In the second stage, up to 5 early stage ALS patients will be recruited and go through the same steps of training and device use.
 
Any feedback or safety concerns raised during the first stage of recruitment of healthy volunteers will be considered before moving forward to the second group of ALS patients.

	
The overall duration of participation for each subject will be up to 3 weeks.
 
The place: Rambam health care campus.
 
Each subject will go through a series of 4 meetings (2 meetings per week), and up to 3 hours per meeting. Meetings will be accompanied by company representatives and/or trained study team.
 
Procedure will consist of an introduction and demonstration of the device features followed by actual use of the device by each subject (including control of gestures, use of menus, activation of pre-defined modes and writing full sentences). User feedback/questionnaire will be completed after the 2nd and 4th session.
 
The user's ability to perform each of the pre-defined tasks, will be measured in each session. In addition, success rate and measured time for completion of pre-defined tasks, collected after the 4th session, will be compared to the success rate and times collected in previous sessions.

Patient Population:	
The subject population is divided into two groups:
 
 
1. Healthy volunteers- up to 10 subjects
 
2. Early stage ALS patients – up to 5 early stage ALS patients that can still communicate orally.
 

No. of Subjects/Sites:	1 site - Rambam Health Care Campus
Study duration:	
Screening: one day.
 
Procedure: 4 sessions of about 2.5-3 hours for each participant, performed over 2 weeks' time.
 
Follow up: none.

Endpoints	
Primary endpoint:
 
Assessment of the feasibility of the use of EyeControl device, measured by:
 
 
• Ability to perform device features: 
 
○ Controlling the EyeControl's Joystick [measured by successful correct performance of over 70% of the gestures].
 
○ Controlling the Rest mode and Siren mode [measured by successful correct performance of over 70% of the gestures].
 
○ Testing the logic of the pre-defined sentences; 
 
a. ability to say 10 pre-defined sentences [over 80% success rate];
 
 
 
 
 

	
b. Time - perform each sentence in less than 2 minutes – [over 80% success rate for all sentences].
 
 
○ Controlling the application and Free text features –words per minute, using the application Alphabet
 
• Required Training time/ learning curve of; 
 
○ pre-defined device features [selected results after the 4th meeting compared with results results of previous meetings]
 
○ free speech [selected results after the 4th meeting compared with results after the 3rd meeting]
 
 
 
• Usability feedback (user experience) questionnaire completed by each user.
 
 
Secondary endpoints:
 
Clinical Safety assessment, measured by number of device related adverse events.

Inclusion criteria	
 
1. Subjects 18 to 65 years old
 
2. Subject with understandable speaking communication
 
3. Subject fluent in Hebrew (speech and writing skills)
 
 
Additional inclusion criteria for Stage 2 of the study:
 
 
4. Subjects with early stage ALS diagnosis – whose speech capability is unaffected
 

Exclusion criteria	
 
1. Subjects with glasses or contact lenses
 
2. Subjects with eye conditions such as Ptosis, Strabismus And Crossed Eyes
 
3. Medical history of epilepsy
 
4. Subjects who according to investigator's judgement, are unable to comply with the requirements of this protocol
 
5. Pregnant or lactating women
 

## 1 INTRODUCTION

### 1.1 BACKGROUND-ALS

Amyotrophic Lateral Sclerosis (ALS, also known as Lou Gehrig's disease) is an adult-onset, fatal neurodegenerative disease. The disease is characterized by degeneration of motor neurons in the primary motor cortex, brainstem and spinal cord, leading to progressive weakness and atrophy of voluntary skeletal muscles. It is recognized as a multi-system disorder. In about a quarter of ALS patients, the disease is associated with subtle cognitive deficits.

The majority of patients die within 3-5 years from disease onset, usually from respiratory failure. Only about 10% of the patients survive for more than a decade.

ALS exhibits phenotypic heterogeneity. Most ALS cases are sporadic, with unknown etiology, whereas 10-15% are familial with clear genetic background – both types are clinically indistinguishable and share several pathogenetic pathways. The incidence of sporadic ALS is 1-2 per 100,000 person-years with an estimated lifetime risk of 1 in 400. The mean age at onset for sporadic ALS is 58-63.

There is no cure for ALS. Riluzole is the only FDA approved drug – which appears to prolong ALS survival by 3 months on average.

Almost all people with amyotrophic lateral sclerosis (ALS) experience a motor speech disorder, such as dysarthria, as the disease progresses. At some point, 80 to 95% of people with ALS are unable to meet their daily communication needs using natural speech.

### 1.2 OTHER “LOCKED IN”

Neurodegenerative and cerebrovascular diseases often lead to deterioration of motor function in patients. These diseases impair traffic capacity, but in some cases they do not harm the mind and cognitive function

These diseases lead to involuntary loss of ability to exercise the muscles of the limbs and the ability to speak, preserving eye movement function. Since in most cases the patient's cognitive function is not impaired, but given their lack of ability to exercise the muscles, they lose their ability to interact with their environment. These patients are defined as “Locked In” as they are imprisoned in their own bodies.

Among these diseases and injuries are stroke of the posterior circulation, MJD (Machado-Joseph disease) and other degenerative diseases such as MG, MS, some of the muscular dystrophies and Parkinson's disease in some cases. Events such as traffic accidents and other accidents also bring patients to such situation, making them arget population for our proposed solution. Each segment of the target population, as a standalone, is relatively small, and therefore there are no available appropriate

 **Communication Support for People with ALS**- David Beukelman, Susan Fager, and Amy Nordness

solutions. However, looking at all patients within the different categories above as a whole, there is a large common denominator and significant demand which our generic systems can address.

### **1.3 THE SOLUTION**

Today, the major leading company that controls the communication devices market is the Swedish company "Tobii". "Tobii" offers a "high-end" technology to the clients, with a variety of products for the fields of gaming and assistive technology.

**Tobii's** Assistive technology - Tobii products are designed to allow control over the computer via Eye tracker.

The company offers several products: The EyeMobile and the PCEye GO, allowing controlling the computer using the eyes, but they restrict movement - every movement requires re-calibration by another (healthy) person (an assistant) and the device must be connected to the computer and to the power supply. This is an expensive technology that requires learning, training and maintenance, as well as third-party assistance per session.

Two other devices that Tobii offers are the I12 and I5. These devices enable communication via tablets, with a 24-hour battery. These two products enable mobility on the one hand but on the other hand all other faults such as the need for re-calibration, high price and the limitation of "environmental restrictions"(Inside the shower, at bed, etc.). These devices cost even more and can sum up to 14,000\$ per unit. The "low cost" mobile solution that Tobii offers is a tablet based on Microsoft hardware with the Tobii software installed on it. This product costs about \$4,000 and still has the same problems such as the need of calibration by third party and the dependent in the screen.

Today, Tobii as a huge company in the field of Eye Tracking offers low cost devices for Eye Tracking in the field of gaming although when coming to the field of assistive communication devices field they use "high end" hardware and a screen as hardware and hours of developing to reach Tobii specific software which is estimated around \$2,000-3,000 per unit (including Tobii's eyetracking camera). This situation takes out automatically many clients who can't afford buying those products (most of the clients) and also doesn't solve the necessary to communicate anywhere, anytime

The EyeControl solution is a set of glasses which are connected to an infrared camera detecting the movement of the pupil and blinks.

The camera connects to a small computer, "Odroid", which is connected to a speaker. The computer translates the pupil's movements and gives an audible sound environment. In addition, by broadcasting through Bluetooth, the patient can use various applications on their smart phone to communicate with others. An outstanding benefit is the fact that the calibration of the pupils is automatic process based on an algorithm without the need for outside aid.

The Product is based on an innovative technology that enables the eye to function as a joystick. The product is innovative (being **portable**), significantly cheaper than other products on the market, comfortable (automatic calibration and independence), Mobile (glasses and a tiny small computer), and allows the patient to communicate with the environment anywhere and anytime. **This is a revolution for patients and their surroundings – the possibility to return to social activity regaining independence and the ability to communicate with the environment.**

The solution developed consists of 3 levels: a call for help, choosing from pre-defined phrases (English and Hebrew) and composing sentences using a virtual board with the alphabet encoding. All these can be played over the loudspeaker while the user is able to hear with headset every letter/word/sentence before he chooses\ it, so that the user doesn't need the screen in front of him.

[figure not shown]

Chart 1: The product

#### 1.4 STUDY RATIONALE

As discussed above, validity of this concept of eye tracking devices used for “locked-in” patients, such as ALS patients, have been proved and is vastly used on the market today. The EyeControl device is indicated for the same group of patients, but due to its size and ease of mobility will allow patients the possibility to return to social activity regaining independence and the ability to communicate with the environment.

#### 1.5 STUDY JUSTIFICATION

The justification for the experiment is based on the fact that the group of people tested are cognitive in the same status of the ALS patients that will be the final user of the product. Moreover, the product is being tested on an early stage ALS patients.

In order to minimize possible risks prior to clinical application, Eyefree Ltd. designed and performed verification and validation tests for the EyeControl device. The testing

included aspects of the device's clinical safety, production and software and quality assurance.

## 1.6 STUDY OBJECTIVES

To demonstrate the safety and feasibility of the EyeControl device in healthy volunteers, and ALS patients in early stages.

## 1.7 STUDY ENDPOINTS

### Primary endpoint:

Assessment of the feasibility of the use of EyeControl device, measured by:

- **Ability to perform device features:**
  - Controlling the EyeControl's Joystick [measured by successful correct performance of over 70% of the gestures].
  - Controlling the Rest mode and Siren mode [measured by successful correct performance of over 70% of the gestures].
  - Testing the logic of the pre-defined sentences;
    - a. ability to say 10 pre-defined sentences [over 80% success rate];
    - b. Time - perform each sentence in less than 2 minutes – [over 80% success rate for all sentences].
  - Controlling the application and Free text features –words per minute, using the application Alphabet
- **Required Training time/ learning curve of;**
  - pre-defined device features [selected results after the 4th meeting compared with results results of previous meetings]
  - free speech [selected results after the 4th meeting compared with results after the 3rd meeting]
- **Usability** feedback (user experience) questionnaire completed by each user.

### Secondary endpoints:

Clinical Safety assessment, measured by number of device related adverse events.

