## 2 STUDY DESIGN

This will be a single center, single arm, open label, prospective study.

The study will be conducted in 2 enrollment stages. Initially, up to 10 healthy volunteers will be recruited and go through a short training for the use of the device followed by actual controlled use of several hours. In the second stage, up to 5 early stage ALS patients will be recruited and go through the same steps of training and device use.

Any feedback or safety concerns raised during the first stage of recruitment of healthy volunteers will be considered before moving forward to the second group of ALS patients.

The overall duration of participation for each subject will be up to 3 weeks.

The place: Rambam health care campus.

Each subject will go through a series of 4 meetings (2 meetings per week), and up to 3 hours per meeting. Meeting will be accompanied by company representatives and/or trained study team for support and guidance in each session..

Procedure will consist of an introduction and demonstration of the device features followed by actual use of the device by each subject (including control of gestures, use of menus, activation of pre- defined modes and writing full sentences). User feedback/questionnaire will be completed after the 2nd and 4th session.

The user's ability to perform each of the pre-defined tasks will be measured in each session. In addition, success rate and measured time for completion of pre-defined tasks, collected after the 4th session, will be compared to the success rate and times collected in previous sessions.

For detailed study procedures refer to section 4, as well as appendix A.

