### 3.5 REMOVAL, REPLACEMENT, OR EARLY WITHDRAWAL OF SUBJECTS FROM TREATMENT OR ASSESSMENTS

Subjects are free to discontinue their participation in the study at any time and without prejudice to further treatment. The investigator must withdraw any subject from the study if that subject requests to be withdrawn.

The subject's participation in this study may be discontinued due to the following reasons:

- Request of regulatory agency, or sponsor or primary care physician or investigator
- Subject withdrew consent
- AE
- Investigator decides that withdrawal from the study is in the best interest of the subject.

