## 6.2 RISKS

**1. Infra-Red Radiation:** the cameras has 4 LEDs with 850 nm wave length- and the risk is that the waves transmitted will heat the eye and by that will cause damages to the user- **This risk was tested by the SII .**

**2. Electricity damages:** the hardware of the device is composed from a battery, Odroid U3 and a speaker which can all go through an electricity damage. All the products are off the shelf products, **bearing CE mark.**

**3. Parts falling apart:** The device is not a one product device yet- so pieces of the device can be split- this risk may cause damages in a very specific conditions. – **We are creating a custom made boxes (3D printer) for the battery and the additional hardware which shouldn't be exposed.**

**4. True Emergency situations** – In cases the user truly needs to call for help and the device doesn't work. **Our pilot involves only users who can communicate without any communication device.**

**5. Allergy to the device** - In case the user has allergy to the device material (plastic, wires etc') in this case the patient will be switched.

Anticipated clinical risks to the participants, based on the above hazards may be (but not limited to); headache, nausea or dizziness caused by the multiple required eye-movements, local irritation due to allergy to device materials (glasses), burning sensation in the eyes.

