## 7.2 ADVERSE EVENTS CLASSIFICATION

AEs reported by the subject or observed by the investigator will be individually listed on an adverse event form in the CRF as follows: the specific event or condition, whether the event was present pre-study, the dates and times of occurrence, duration, severity, relationship to study device, specific countermeasures, and outcome.

Note: Event which was present pre-study is not considered as an adverse event unless it has worsened since the enrollment to the study.

All AEs will be characterized by the following criteria:

- Intensity or Severity
- Relatedness
- Outcome
- Treatment or Action Taken

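### The only safety endpoint is an event count, which varies with subjects and sessions and gives neither the share of users affected in each group nor the stops due to adverse events

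*Protocol*

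**What the plan says.** The objective in Section 1.6 is "To demonstrate the safety and feasibility of the EyeControl device in healthy volunteers, and ALS patients in early stages". Safety is thus half of the objective, for two named populations. The only safety endpoint, in Section 1.7 and in the same words in the synopsis, is "Clinical Safety assessment, measured by number of device related adverse events". It names no subject or session denominator and no group, and it does not mention stops.

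The size of the study is not fixed. Section 2 says "Initially, up to 10 healthy volunteers will be recruited" and, for the second stage, "up to 5 early stage ALS patients will be recruited". Planned exposure is also in Section 2: "Each subject will go through a series of 4 meetings (2 meetings per week), and up to 3 hours per meeting". Section 3.5 says that "participation in this study may be discontinued due to the following reasons", and an adverse event is one of those listed. Under Section 3.4 a subject is enrolled at first use of the device, so someone who stops during the first meeting stays in the study population.

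Section 6.2 anticipates "headache, nausea or dizziness caused by the multiple required eye-movements", local irritation and burning eyes. Adverse events are recorded at every meeting (Sections 4.2 to 4.5, Appendix A). Section 7.2 has each one listed individually with, among other items, "the dates and times of occurrence, duration, severity, relationship to study device". Section 3.6 puts the reason for study exit on the CRF. Section 9 addresses sample size only.

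**The concern.** A number of events answers how much was reported, not how many users were affected. In this design the two can part for three reasons.

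- The total falls when fewer subjects are enrolled or fewer sessions held, with no change in how the device is tolerated.
- The anticipated symptoms come from use and can recur at each of four meetings, so one susceptible person and several mildly affected people can produce the same total.
- An adverse event can end participation, so the outcome may shorten the exposure over which it is counted, and the endpoint does not show that this happened.

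At stake is the safety half of the objective. A reader of the result would want to know what fraction of healthy volunteers, and of ALS patients, had a device-related event, and whether anyone stopped because of one. The stated metric gives neither.

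**Working it through.** The protocol states no adverse event rate, power or precision figure for safety, so there is nothing to reproduce. The calculations below are illustrations.

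**Inputs from the protocol.** At most 10 + 5 = 15 subjects; 4 meetings each; at most 15 × 4 = 60 subject-sessions.

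**Assumptions not in the documents.** At most one device-related event per session attended, with constant probability p from 0.1 to 0.5. Probability s, from 0 to 1, that a subject stops after an event.

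**Step 1: what a given count says about users.** Take an illustrative count of 4. If recurrences are counted, it may come from one subject affected at all four meetings; otherwise it may come from up to four subjects. Exact (Clopper-Pearson) 95% limits for x of n are the 2.5% quantile of Beta(x, n − x + 1) and the 97.5% quantile of Beta(x + 1, n − x):

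| Subjects affected | Proportion | Exact 95% CI |
|---|---|---|
| 1 of 15 | 6.7% | 0.2% to 31.9% |
| 4 of 15 | 26.7% | 7.8% to 55.1% |
| 1 of 5 (all events in ALS patients) | 20% | 0.5% to 71.6% |
| 4 of 5 (all events in ALS patients) | 80% | 28.4% to 99.5% |

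**Step 2: dependence on enrolment.** With no stopping, the expected count is N × 4 × p. At p = 0.2 this is 15 × 4 × 0.2 = 12.0 for 15 subjects, but 11 × 4 × 0.2 = 8.8 if only 11 enrol (an assumed shortfall). If a recurring symptom counts once per subject, the expected count is N × [1 − (1 − p)^4]: 15 × 0.5904 = 8.9 against 11 × 0.5904 = 6.5. The count falls under either counting rule, although the harm per user is the same.

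**Step 3: dependence on stopping, if each recurrence counts.** The expected count is 15 × Σ p(1 − ps)^k for k = 0 to 3. The expected number of subjects with at least one event is 15 × [1 − (1 − p)^4].

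| p | Count, s = 0 | Count, s = 0.5 | Count, s = 1 | Fall, s = 0 to s = 1 | Subjects with ≥ 1 event, any s |
|---|---|---|---|---|---|
| 0.1 | 6.0 | 5.6 | 5.2 | 14% | 5.2 |
| 0.2 | 12.0 | 10.3 | 8.9 | 26% | 8.9 |
| 0.3 | 18.0 | 14.3 | 11.4 | 37% | 11.4 |
| 0.5 | 30.0 | 20.5 | 14.1 | 53% | 14.1 |

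Events per session attended stay at p for every s. The subject-level number does not move with s because, in this model, stopping follows the first event.

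**Step 4: the other counting rule.** If a recurring symptom counts once per subject, a subject who stops after one event and a subject with the same symptom at all four meetings each contribute 1, and the effect in Step 3 disappears for that symptom. The protocol does not state which rule applies.

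**The case against.** The strongest reply is that the protocol need only name the variable. Tabulation by event, subject or group is commonly left to a statistical analysis plan, which is not shown, and nothing in Section 1.7 says that the result will be one pooled total. That is fair as regards tables and intervals. It does not remove the point, because the protocol does not leave the measure open: it states that safety is measured by a number of events. Further tables would sit beside that endpoint without changing it.

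Two stronger readings are tempting. A reader might infer that intolerance necessarily lowers the reported harm. That needs every recurrence to count as a new event, which no section states. It also needs the most affected subjects to leave, whereas Section 3.5 says only that participation may be discontinued. Even then it would be true of this one number only, because severity and exit reason are recorded for each subject.

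A reader might also infer that the endpoint could rank a poorly tolerated device as the safer one. The study has a single arm, and no safety threshold is tied to the count. Under Section 2 the move to the ALS stage follows consideration of any feedback or safety concerns, and under Section 3.7 suspension follows suspicion of unacceptable risk. Nothing is ranked.

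Two further objections stand. With at most 15 subjects, individual listings allow everything above to be rebuilt. And the number of subjects with an event does not by itself show that an early stopper fared worse, so severity and stops have to be reported as well.

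**Conclusion.** The point holds as a weakness of the endpoint metric, not as a loss of data. Three limits follow from the wording and the design alone: an event count varies with the number of subjects and sessions, it does not give the share affected in either group, and it does not show stops due to adverse events.

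The effect of early stopping is conditional. It requires recurrences to be counted per session, and its size rests on assumed event and stopping rates. If every subject stopped after a first event, the expected count would fall from 6.0 to 5.2 at p = 0.1 and from 30.0 to 14.1 at p = 0.5. With rare events or rare stopping it is small. The intervals for a count of 4 are likewise illustrative. The change is worth making because it is cheap and safety is half of the objective, but nothing in the conduct of the study depends on it.

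**What to change.** Restate the secondary endpoint, in Section 1.7 and the synopsis, as the number and proportion of enrolled subjects with at least one device-related adverse event, separately for healthy volunteers and ALS patients, with exact 95% confidence intervals labelled as descriptive. Report beside it:

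- the highest severity per subject;
- the number of subjects who stopped because of a device-related adverse event;
- the event count with the number of sessions attended, and a statement of whether a symptom that recurs at a later meeting is a new event.

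The sessions attended matter for the proportion too, since a subject who leaves for an unrelated reason has fewer chances of an event.

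The cost is a change of wording and one small table. Severity, relationship and exit reason are already on the CRF, and attendance follows from the visit records. Device use, discontinuation and subject management are untouched. The downside is that the imprecision becomes visible. Even with no affected subject, the upper exact limit, 1 − 0.025^(1/n), is 30.8% at n = 10 and 52.2% at n = 5.
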